14. PROVISIONS TO MONITOR THE DATA TO ENSURE THE SAFETY OF SUBJECTS*

Throughout course of a study subject's participation in the study they will be followed for signs of adverse events to medication administration or for complications of capsule endoscopy. Adverse events will be documented as part of initial data analysis. This data analysis will be performed by the residents and fellows who are part of the study staff for this project. Given that we anticipate minimal adverse events, any adverse events that occur will be reviewed by the study staff and the Primary Investigator within one week. This would include a complete analysis of the how the adverse event occurred in order to help prevent further events going forward. At that time the Primary Investigator will also assess cumulative reports.

We will set up a DSMB to review the adverse events and the primary aim. Risk associated with early discharge will be monitored closely, e.g. bleeding immediately after discharge

- A statistician at the UMass Medical School, a clinician inside and one outside UMass
- Review of data will be performed at the mid-point of the study
- See attached charter.

15. WITHDRAWAL OF SUBJECTS WITHOUT THEIR CONSENT*

If the patient is unable to swallow the capsule we would remove them from the study.

Patients will be withdrawn from study if the bleeding source is found to be outside of the stomach or intestines.

A subject can withdraw from the study at any time per their request.

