4. OBJECTIVES*

- 1) The objectives of this study are to compare the efficacy of video capsule endoscopy (VCE) as first line vs the standard of care workup of H [upper endoscopy] and NHGIB by endoscopy [upper, lower and other tests] in the rate of detection of active bleeding in patients admitted to the clinical decision unit (CDU). We propose to examine differences in time to detection of active bleeding, diagnosis, reduction in numbers of procedures, hospital costs and length of stay between a conventional workup protocol and our proposed protocol of early capsule endoscopy deployment. All patients in the SOC group will be admitted to the

INVESTIGATOR STUDY PLAN - H00015196

hospital. These will be compared to those in the VCE first group who are stable and may be discharged from the CDU directly.

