5. BACKGROUND*

After 40 years of considering gastrointestinal bleeding as upper or lower and largely ignoring the small intestine, there is accumulating evidence that the conventional approach to the assessment of NHGIB could be improved by early deployment of a video capsule as the first diagnostic test. Currently, video capsule endoscopy is considered the gold standard diagnostic test for small intestinal bleeding after upper and lower endoscopy. However, we feel that video capsule endoscopy is an underutilized, minimally invasive tool that can improve rates of detection, minimize patient discomfort, and shorten the length of hospital stay for many patients. In a recent study at UMass of 336 patients who presented to the ED with complaints of gastrointestinal bleeding only 36 patients (10.7%) were given a video capsule during their stay.¹

Traditionally, in patients with hematemesis, upper endoscopy has been the diagnostic and therapeutic modality of choice. However, recent data from a randomized clinical trial by Sung et al suggests that when video capsule endoscopy is used as the primary diagnostic tool, the investigators were able to safely define those patients that require admission from those that can be discharged for later follow-up². In this cohort, 30% of patients could be safely discharged and undergo endoscopy, if necessary within 48 hours, as an outpatient. This data is consistent with our internal epidemiological data from UMass where nearly 30% of patients who were admitted did not receive any endoscopic evaluation as in-patients.

Similarly, in a randomized controlled trial, we have recently shown that patients with NHGIB may benefit from early VCE. In this population, the detection of active bleeding with video capsule as the first procedure was 63% compared with 27% for the standard of care approach. We did not demonstrate a significant reduction in length stay since this was not part of the trial design. No attempt was made to change physician behavior. The study was too small to demonstrate a reduction in procedures, but there was a modest reduction in healthcare costs despite the addition of the video capsule. We encountered no adverse events in the study. Readmission rates were not significantly reduced but there were no readmissions in the capsule group for G.I. bleeding where there were four in the standard of care group.

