Our hypothesis is that both signs and symptoms provide poor localization as to the origin of bleeding in NHGIB. Data from our previous study suggests that the ingestion of a video capsule in the emergency department could quickly and non-invasively provide clinicians accurate data as to the origin of the bleeding. This information could provide a guide to further management of the patient. Video capsule endoscopy is able to visualize bleeding in the esophagus, stomach, duodenum, small intestine and right colon, thereby eliminating the guess work of deciding which endoscopic approach to use.

We plan to use the clinical decision unit for two reasons. This unit provides an ideal site for the early safe deployment of a video capsule or initiation of a standard of care workup for either or NHGIB. Second, in those patients who are demonstrated not to be bleeding

INVESTIGATOR STUDY PLAN - H00015196

in either group by capsule endoscopy or standard of care workup may be discharged home safely without being admitted, thereby saving significant costs. It is known that 80% of patients stop bleeding spontaneously. Thus, the earlier they are examined the more likely the origin of the bleeding is likely to be found and appropriate management instituted

The use of capsule endoscopy has been approved by the FDA since 2001 for small intestinal bleeding obscure GI Bleeding. It is very safe, no deaths associated with its use have been reported. More than 3 million capsules have been deployed and obstruction and perforation are extremely rare.

Interest in the broader use of VCE is accumulating. In 2004 Sachdev et al reported a pilot study on the use of early use of VCE in acute NHGIB. This showed a 50% reduction to time to diagnosis in 24 patients. More recently studies of VCE deployed in the ED, in patients with upper GI bleeding showed improved management. Our group recently demonstrated that the closer a video capsule is performed to the time of bleeding the higher the likelihood of locating the sources and the higher the therapeutic intervention rate.³

This protocol is logical step to prospectively examine this concept in a large randomized prospective trial for both H and NHGIB. The questions are, can early capsule intervention decrease time to diagnosis, numbers of procedures, admission rate and hospital length of stay in patients with H and NHGIB.

References:

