11. PROCEDURES INVOLVED*

Screening

- Patients presenting to the Emergency Room with H or NHGIB (defined as hematemesis, or melena or hematochezia respectively or severe anemia) will be identified by a member of the ED staff and triaged to the CDU for stable patients or ICU for unstable patients.

Once a subject is identified a page will be sent to a member of the research team (i.e, research staff member, GI fellow on call, or GI attending on call) from the CDU. In addition to this, the clinical research coordinator and or GI fellow will screen the Emergency Department triage software for patients who are listed as having NHGIB. Based on prior experience of our randomized trial we expect for every 3 patients asked to participate in the study, there will be 1 patient who agrees to participate. In the Emergency Department study already cited, the Emergency Department at UMass sees about 350 patients annually for GI bleeding. Of these patients, approximately 230 patients have NHGIB and 120 have hematemesis. Given the 3:1 screening ratio, we would expect approximately 40 to be enrolled for the H and 40 patients for the NHGIB patients every year who agree to participate in the study. In 24 months, we would expect to recruit up to 160 patients to our study, 80 for the H and NHGIB respectively. Once a subject is identified the subject will then be seen and examined by the GI fellow and attending as per standard of care and asked to participate in the study.

[figure not shown]
Randomization:

- If inclusion/exclusion criteria are met, the consent discussion takes place and only if the subject agrees and consent is obtained, then the subject is randomized to the “Early Capsule Group” or “Standard of Care Group.” All patients in the “Early Capsule group” will receive the video capsule. A few of the patients in the “Standard of Care Group” may receive the capsule as indicated by what is considered the standard workup.

INVESTIGATOR STUDY PLAN - H00015196

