- We will assign patients to study ID numbers consecutively by the order of which they are enrolled in our study. For the Randomization Process we will be utilizing a random sorting generator to assign integers in a random order, corresponding to study IDs which allows researchers to randomly assign study participants into specific study groups. The same process would apply to the H and NHGB groups, but each of these groups will have separate randomizations. Assignments are put into a mail merge, locked with a password, and printed, then put into a sealed, security envelope, which is sealed with a Study ID sticker. The Randomization Scheme will allow us to attach particular Study ID numbers randomly to particular groups based on our criteria to have 40 subjects in the early capsule group and a comparable number in the Standard of Care SOC workup arm for both the H and NHGIB groups. The envelope is only opened once all entry criteria have been met and the subject will be assigned a group/arm. Subjects with a Study ID ending in 1-80 will be enrolled in the H group. Subjects with a Study ID ending in 100-180 will be enrolled in the NHGIB group.
- We plan to enroll up to 160 subjects in our study. 40 subjects will be randomized to the “early capsule” deployment group and 40 in the SOC arm for H patients. A similar allocation will apply to the NHGIB group with 40 patients in each arm. This means that this group of subjects will have a VCE deployed as soon as possible after presentation to the ED and CDU, once the consent process has taken place, eligibility has been confirmed, and the subject has met the standard of care guidelines for preparation before capsule ingestion. Standard preparation for capsule ingestion means that a patient cannot eat for 10 hours prior to deployment of the capsule. Therefore, patients in our study will be asked when they had last eaten. If patients report that they have not eaten anything over the past 10 hours we will deploy the capsule immediately. If, however, patients say that they have eaten something over the past 8 hours we will take note of when they believe they last ate and will deploy the capsule 8 hours after the time that they last ate. In our previous ED study, no patients in the early capsule arm had food in the stomach on capsule examination.

INVESTIGATOR STUDY PLAN - H00015196

[figure not shown]

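### Section 15 removes patients after randomisation, by one rule that falls mainly on the capsule arm and one that depends on the work-up result, and no public text keeps them in the analysis

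*Protocol*

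**What the plan says.** Protocol Section 15 gives two rules for taking patients out without their consent. Rule 1: "If the patient is unable to swallow the capsule we would remove them from the study". Rule 2: "Patients will be withdrawn from study if the bleeding source is found to be outside of the stomach or intestines".

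Both act after allocation. Section 11 states: "The envelope is only opened once all entry criteria have been met and the subject will be assigned a group/arm". Swallowing the capsule and searching for a source come later.

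The arms differ in exposure to both rules. Section 11 gives the capsule to all early-capsule patients, whereas a few SOC patients "may receive the capsule as indicated by what is considered the standard workup". Section 4 describes the comparator as "the standard of care workup of H [upper endoscopy] and NHGIB by endoscopy [upper, lower and other tests", so the test that reveals the source also differs by arm.

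Section 10 makes time to detection of active bleeding or stigmata of recent bleeding the primary endpoint. Section 13 lists chi-square tests, t-tests and Kaplan-Meier curves for two cohorts. It names no analysis set and gives no rule for the data of removed patients. Sections 13 and 25 raise 36 per arm to 40 to allow for technical failures and incomplete studies, without saying whether such patients are analysed. The document posted as the SAP is a DSMB charter. Its Section 9 calls for review of a SAP before data are presented, but that SAP is not in the file.

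**The concern.** Randomisation makes the arms comparable only if everyone randomised is counted. Rule 1 selects on an event that nearly always needs a capsule to occur, so it thins one arm and hardly touches the other. Rule 2 selects on what the work-up finds, which is closely tied to the primary endpoint and is reached by different tests in the two arms.

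If Section 15 is followed as it reads and removed patients leave the dataset, the analysis compares capsule patients who could swallow and had an in-scope source with a differently selected SOC group. That affects time to detection and every secondary endpoint: admission, length of stay, procedures, transfusion, complications, costs and readmission. A failed swallow is also part of what a capsule-first policy delivers, so removing those patients hides one of its costs.

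**Working it through.** **The plan's own allowance.** 36 / (1 - 0.10) = 40; the 10% is implied, not stated. 40 x 2 arms x 2 bleeding groups = 160, as planned. Assuming a two-sided 5% test of 63% v 27%, power is 0.914 with 40 per arm and 0.883 with 36. The extra patients therefore protect power. They do nothing about selection, because they do not restore the patients removed.

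**Exposure to rule 1.** Capsule arm: 40 of 40 in each bleeding group. The plan gives no figure for capsule use in the SOC arm, so these are proxies only:
- Section 11 expects 4-10% small intestinal bleeding: 0.04 x 40 = 1.6 to 0.10 x 40 = 4.0 patients. This could be too low, since a capsule may also be given and show nothing.
- Section 5 reports that in an emergency department cohort of 336, "only 36 patients (10.7%) were given a video capsule during their stay": 0.107 x 40 = 4.3 patients.
- For hematemesis the SOC test is upper endoscopy, so exposure is probably close to nil.

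**Effect on time to detection.** Let F_s(t) and F_n(t) be the proportions detected by time t among capsule-arm patients who can and cannot swallow. With k of 40 unable to swallow, no censoring and no SOC removals:
- all kept: [(40 - k) F_s(t) + k F_n(t)] / 40
- non-swallowers dropped: F_s(t)
- shift from dropping: (k/40) x [F_s(t) - F_n(t)]

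The shift favours the capsule at any time when non-swallowers lag behind. If both groups end at the same proportion but non-swallowers get there later, the shift is zero at the end and positive before it. The capsule curve still looks faster than it should.

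**Bound on the proportion ever detected.** The bracket cannot exceed 1 in size, so the shift is at most 1/40 = 2.5 points per dropped patient. This needs no detection rate and so holds for hematemesis too.

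**Illustration, NHGIB only.** Section 5 reports that "the detection of active bleeding with video capsule as the first procedure was 63% compared with 27% for the standard of care approach". Take 63% as the rate after removal and assume no non-swallower is detected later. The difference with failures dropped is 63 - 27 = 36.0 points.

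| Assumed failures k | Capsule rate, all kept | Difference, all kept | Overstatement if dropped |
|---|---|---|---|
| 1 | 39 x 0.63 / 40 = 61.4% | 34.4 | 1.6 |
| 2 | 38 x 0.63 / 40 = 59.9% (59.85) | 32.9 (32.85) | 3.2 (3.15) |
| 4 | 36 x 0.63 / 40 = 56.7% | 29.7 | 6.3 |

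These figures are for active bleeding, without stigmata, and for a proportion rather than a time to event. They show scale only.

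**Rule 2.** The documents give no frequency, so no arithmetic applies. Set side by side, the passages conflict. Rule 2 read literally covers an esophageal source, whereas Section 5 says "Video capsule endoscopy is able to visualize bleeding in the esophagus, stomach, duodenum, small intestine and right colon" and Section 11 has a next step for blood found in the esophagus.

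**The case against.** The best case against the point has four parts.

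- **Removal from the study is not exclusion from the analysis, and the missing SAP may settle it.** This stands as a limit. What can be said is that no public text keeps these patients in; a reader might infer that bias will occur, and the documents do not show that.
- **Removals should be rare.** Section 6 excludes dysphagia at presentation. Section 28 mentions inability to swallow, but no rate is given. Four failures would use up the whole 36-to-40 allowance, which is meant to cover other losses too, and endoscopy remains open to patients who cannot swallow. This stands and keeps the expected size small.
- **The effect looks harmless if non-swallowers are eventually detected as often as the rest, or because a large difference would stay significant.** A reader might infer either, but neither carries over to the primary endpoint. Equal but later detection still flatters the capsule on time to detection. Significance in one large-effect comparison of proportions (Fisher p = 0.0025 for 23/36 v 11/40 with failures dropped, 0.0123 for 23/40 v 11/40 with them kept) says nothing about the Kaplan-Meier comparison or smaller effects. As a worst case with no true difference, dropping four capsule-arm non-detections takes the chi-square type I error from about 0.05 to 0.064, 0.082 or 0.115 at common rates of 27%, 45% or 63%. That is an extreme, not an estimate.
- **Rule 2 probably means sources outside the digestive tract, loosely worded.** This is plausible, because other sections treat the esophagus as a study location. A reader might infer that esophageal bleeders will in fact be withdrawn; the text does not establish that. It establishes a contradiction to be resolved.

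**Conclusion.** The point holds and should be fixed. Both rules take patients out after randomisation, rule 1 is unequal by arm, rule 2 turns on the work-up result, and no public text keeps these patients in the analysis. If they are dropped, every endpoint loses its randomised comparison.

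The practical size is probably small for rule 1. It depends on an unstated swallow-failure rate and on when and how often non-swallowers are later detected. The direction favours the capsule if they are detected later or less often than swallowers. The calculations assume complete follow-up and no SOC removals, and the illustration does not measure the primary endpoint. For rule 2, neither size nor direction can be derived. The conclusion about public text is firm; whether bias will arise depends on a SAP that cannot be seen.

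**What to change.** State in Sections 13 and 15, and carry into the SAP:

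- All randomised patients are analysed in their assigned arm for all endpoints, separately for H and NHGIB. Time runs from the same origin in both arms; Section 11 already records time from entry to the emergency department and CDU.
- Patients who cannot swallow the capsule stay in, with detection by any later test counted when it occurs.
- Patients withdrawn under rule 2 also stay in. Section 10 names no anatomical location, so say in advance, identically for both arms, whether such a finding is an event. If it is not, keep them in the risk set as not detected to the end of a common follow-up window. Censoring them when the finding is made would let the result of the work-up decide who leaves the risk set.
- Outcomes are collected through the 30-day call unless consent is withdrawn.
- Any analysis that leaves out technical failures is a sensitivity analysis only.
- The source-location wording in Section 15 is reconciled with Sections 5 and 11.

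The cost is wording and a little more follow-up. The capsule result may look slightly less favourable.

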6. INCLUSION AND EXCLUSION CRITERIA*

Inclusion Criteria:

- Age greater than 18 years old

INVESTIGATOR STUDY PLAN - H00015196

- New onset of hematemesis, melena or hematochezia
- Able to sign consent
- Hemodynamically stable (i.e. blood pressure >100/60 or pulse <110 at the time of consent)
- ED must plan to admit patient to the hospital or Clinical Decision Unit.
- If patients have pacemakers and/or ICD they will be placed on telemetry.

Exclusion criteria:

- Adults unable to consent
- Individuals who are not yet adults (infants, children, teenagers)
- Pregnant women
- Prisoners
- Prior history of gastroparesis
- Prior history of gastric, or small bowel surgery
- Prior history of inflammatory bowel disease
- Concern for infectious colitis
- Evidence of dysphagia at the time of presentation
- Presence of small amounts of bright red blood per rectum
- Allergy to metoclopramide or erythromycin
- Code status of DNR/DNI or CMO
- Prior history of abdominal radiation
- Abdominal pain suggesting an acute abdomen or obstruction. In clinical practice, only patients with crampy abdominal pain due to Crohn's disease, previous intestinal surgery and a previous history of radiation therapy require a patency capsule or CT enterography, before capsule endoscopy.
- Patients who cannot undergo surgery

Subjects who do not speak English may be included if an IRB-approved short form is available for use in their language and interpretation services are available.

7. **STUDY-WIDE NUMBER OF SUBJECTS***

See #25.

8. **STUDY-WIDE RECRUITMENT METHODS***

See #24.

9. **STUDY TIMELINES***

- The participation of individual subjects in this study will be approximately 31-40 days (the length of their hospitalization plus an additional thirty days for follow up).
- The duration anticipated to enroll all study subjects is about 24 months.

INVESTIGATOR STUDY PLAN - H00015196

- The estimated date for the investigators to complete this study and for data analysis is 3 years.

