10. STUDY ENDPOINTS*

- The primary endpoint will be time to detection of active bleeding or stigmata of recent bleeding [blood clot or visible vessel].
- Secondary endpoints will include, admission rate, hospital length of stay, number of invasive procedures, blood product transfusions, number of therapeutic procedures, complication rates, costs of admission, and readmission rates

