The PI or sub-investigator will then view the video of the capsule recording [it takes about 5 minutes to establish if there is bleeding and where it is coming from. More detailed analysis will take about 15-20 minutes]. As soon as the capsule recording has been reviewed, the PI or sub-investigator will inform the patient's attending gastroenterologist on the consult service as to where the bleeding is coming from or that bleeding is not seen, as soon as possible after the video has been reviewed. Depending on the findings a recommendation will be made as to the next most appropriate test. See attached Figure 1. If blood is found in the esophagus, stomach or duodenum an upper endoscopy is recommended. If blood is seen in the small intestine, it will be recommended that the subject next have a push enteroscopy, deep enteroscopy, or angiography. If blood is found in the right colon, colonoscopy may be performed or deferred to colonoscopy as an outpatient, if active bleeding has ceased. If the capsule study is not diagnostic and no blood is seen in the GI tract and there is no ongoing hematochezia, the subject will be placed in ED observation for up to 23 hours and evaluated for potential discharge and follow-up by gastroenterology as an outpatient. If, and as appropriate an EGD or colonoscopy will be performed as an outpatient within 72 hours.

For most subjects, the capsule will pass in a bowel movement within 24 -72 hours of ingestion.

An equal number of subjects [up to 40] will be randomized to the "SOC group." For NHGIB workup may include upper endoscopy, colonoscopy, and additional capsule or small bowel enteroscopy depending on the subject's presentation and the results of the workup performed by the gastroenterology team. For some subjects, the VCE would be done as part of standard of care. We estimate that 4-10% of patients will have small intestinal bleeding. For patients requiring a video capsule endoscopy as part of "SOC workup" the patients will be given the same Olympus video capsule that is used in the "Early Capsule" group. Further management would be as standard of care which requires

INVESTIGATOR STUDY PLAN - H00015196

admission. These subjects will be discharged on the recommendation of the attending hospitalist after completion of treatment.

Review and Follow-Up

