12. DATA AND SPECIMEN BANKING*

Not applicable.

13. Data Analysis and Management*

- Data analysis plan: As discussed above, data will be obtained through review of medical records. Specifically, we will be looking at time to detection of active bleeding or visualization of stigmata of recent bleeding such as adherent blood clot or a visible vessel, laboratory values, number of blood products transfused procedures performed, along with additional measures as described above. Once we have separated our two cohorts we will perform chi-square and standard t-tests to compare the different dependent variables in the two cohorts. We will also perform a Kaplan-Meier curve analyses to compare length of stay and time to diagnosis which is the primary metric of this study.

INVESTIGATOR STUDY PLAN - H00015196

- Steps that will be taken to secure data: All clinical data from individual subjects will be de-identified and given a study number. The study number will serve as a link between the data and the subject's identifiable information. RedCAP online encrypted database will be used to store the dataset. The database will only be accessed by the primary investigator and research assistants.
- Data will be exported for analysis as a de-identified data set. The de-identified dataset (which would be absent of any PHI) will remain at UMass under password access by the PI and sub-investigators.
- Identifier keys will be destroyed once primary data analysis is complete.
- No identifying information will be used in any report or publication generated from this study.
- Power analysis: Based on our recent randomized trial of NHGIB of VCE v SOC, we were able to detect a very significant difference in the rate of active bleeding with 36 patients in each arm, Hazard ratio 2.7. J Sung et al. used the same sample size in their randomized trial for H bleeding to similar effect. We thus plan on using 40 patients in each arm for each group. The increase to 40 from 36 is used to cover any technical failures or incompletely studied patients.

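### Section 15 as worded withdraws randomized patients with an esophageal bleeding source, although Section 6 admits them and detecting their bleed meets the Section 10 primary endpoint.

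*Protocol*

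**What the plan says.** Protocol Section 15 gives the rule without exception: "Patients will be withdrawn from study if the bleeding source is found to be outside of the stomach or intestines".

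Four other sections bear on it:

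- Section 6 defines entry by presenting sign: "New onset of hematemesis, melena or hematochezia". None of the listed exclusions concerns an esophageal source; the nearest is dysphagia at presentation.
- Section 10 defines the outcome without reference to site: "The primary endpoint will be time to detection of active bleeding or stigmata of recent bleeding [blood clot or visible vessel".
- Section 5 lists the esophagus as a site of its own: "Video capsule endoscopy is able to visualize bleeding in the esophagus, stomach, duodenum, small intestine and right colon".
- Section 11 provides for blood found there: "If blood is found in the esophagus, stomach or duodenum an upper endoscopy is recommended".

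Section 11 also plans a telephone call 30 days after discharge to ask about recurrent bleeding. Section 13 does not say whether withdrawn patients are analysed. The DSMB charter, posted as the SAP, mentions withdrawals only as an item in safety summaries that the board may request.

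**The concern.** A patient can present with hematemesis, meet every entry criterion, be randomized, have an esophageal bleed or visible vessel detected, and so reach the primary endpoint. Section 15 as written then requires withdrawal because of that same finding.

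Two features make this more than untidy wording. First, withdrawal comes after randomization. Second, its trigger, locating the source, is close to the primary endpoint itself. Only patients whose source was found can be removed. If the esophageal share of located sources is similar in both arms, more are removed from the arm that finds more. The rule is not limited to the H group: an esophageal source presenting as melena would be withdrawn from the NHGIB group too.

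At stake, if withdrawal means leaving the analysis or follow-up, are primary-endpoint events, the secondary endpoints observed later (such as length of stay and readmission) and the 30-day recurrence data.

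**Working it through.** **Textual check.** Sections 5 and 11 both list the esophagus separately from the stomach, so in the protocol's own vocabulary the words stomach or intestines do not cover it. For a patient with a detected esophageal source:

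| Section | Status of the patient |
|---|---|
| 6, eligibility | admitted |
| 10, primary endpoint | event counted |
| 11, procedures | in-study recommendation made |
| 15, withdrawal | withdrawn |

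No passage limits the Section 15 rule to sources outside the gastrointestinal tract. The contradiction needs no figure to establish it.

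**The plan's own size.** Section 13 takes 36 per arm from the prior NHGIB trial ("difference in the rate of active bleeding with 36 patients in each arm, Hazard ratio 2.7") and raises it to 40. Significance level and power are not stated. Assuming two-sided 0.05 and 80% power, Schoenfeld's formula gives

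events = 4 × (1.960 + 0.842)² / (ln 2.7)² = 31.8, rounded up to 32.

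With the Section 5 detection rates, 32 / (0.63 + 0.27) = 35.6, or 36 per arm, and 36 / 0.90 = 40. This matches the plan, but other standard choices do not (Freedman's formula gives 38 events, or 43 per arm). It is therefore a consistency check, not a reconstruction of the authors' calculation.

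**Illustration of the loss.** Inputs are 40 per arm (Section 11) and detection of 63% with capsule and 27% with standard of care (SOC) (Section 5, prior NHGIB trial). The esophageal share s of located sources is assumed, because the documents give none.

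- Expected events with no withdrawal: 40 × 0.63 = 25.2 and 40 × 0.27 = 10.8, total 36.0.
- Removed, capsule: 25.2 × s. Removed, SOC: 10.8 × s.
- Events left: 36.0 × (1 − s).
- Power at hazard ratio 2.7, two-sided 0.05 (assumed): Φ(√(events/4) × ln 2.7 − 1.960).

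| s (assumed) | Removed, capsule | Removed, SOC | Events left | Power |
|---|---|---|---|---|
| 0 | 0 | 0 | 36.0 | 84.6% |
| 10% | 2.5 | 1.1 | 32.4 | 80.7% |
| 20% | 5.0 | 2.2 | 28.8 | 76.0% |
| 30% | 7.6 | 3.2 | 25.2 | 70.3% |

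**Effect on the contrast.** If withdrawn patients are dropped altogether, the detection rates at s = 10% become (25.2 − 2.52)/(40 − 2.52) = 60.5% and (10.8 − 1.08)/(40 − 1.08) = 25.0%. The difference is 35.5 points, against 36 without withdrawal. At s = 30% the rates are 54.4% and 20.6%, a difference of 33.8 points. On these inputs the main cost is lost events and a population that is no longer the one enrolled; the shift in the contrast is small.

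**The case against.** The best defence is loose drafting. The authors may simply have meant sources outside the gastrointestinal tract. This is a single-centre study, the principal investigator oversees all of it, and investigators read the capsule videos, so the sentence might never be applied against the protocol's own pathway. That may be the intent, but no passage says so, and the rule is worded as mandatory.

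It can also be said that Section 5 only describes what the device can see, in an argument about NHGIB, and that Section 11 concerns where blood is seen and which test follows. A care recommendation followed by study withdrawal is not strictly contradictory. This stands in part: the documents treat the esophagus as in scope rather than naming it as a target, and the sharper conflict is with Sections 6 and 10.

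Two stronger readings are tempting, and the documents do not support them.

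- A reader might infer that events are deleted and 30-day follow-up ends. Section 15 does not say that collected data are discarded, that the patient leaves the analysis or that calls stop. These consequences are conditional.
- A reader might multiply an assumed share by all 40 patients, obtain 4, 8 or 12 per arm at 10%, 20% or 30%, and conclude that a 10% share exhausts the margin of 40 − 36 = 4. That holds only if every patient's source is located, because the rule acts only on sources that are found. At the proxy rates, reaching 4 would take a share of 4/25.2 = 16% in the capsule arm or 4/10.8 = 37% in the SOC arm. The margin is in any case assigned to something else: "The increase to 40 from 36 is used to cover any technical failures or incompletely studied patients".

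**Conclusion.** The point holds as an internal contradiction. As written, Section 15 withdraws randomized patients whom Section 6 admits and whose detected bleed counts under Section 10, in both the H and NHGIB groups. Nothing elsewhere in the protocol or the DSMB charter corrects it.

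The size of the loss cannot be derived from the documents. The illustration, 10% to 30% of expected events with more than twice as many removals in the capsule arm (25.2/10.8 = 2.3), rests on four assumptions: the esophageal share, an equal share among located sources in both arms, detection of active bleeding standing in for finding the source, and NHGIB rates applied to either group. The last is weakest for the H group, where SOC starts with upper endoscopy (Section 4) and the arms may differ less in detection. The loss of events further assumes that withdrawn patients are dropped from the analysis, or censored before their detection counts, which the plan leaves open.

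**What to change.** Reconcile Section 15 with Sections 5, 6, 10 and 11 by limiting the study-withdrawal rule to bleeding sources outside the gastrointestinal tract. State there or in Section 13 that patients with an esophageal source remain in the study, count as detections in the arm to which they were randomized, and complete the 30-day follow-up. Section 13 should also say how any patient still withdrawn under the narrower rule is analysed, since that withdrawal too would follow randomization and depend on finding the source.

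The cost is a short protocol amendment: one changed sentence in Section 15 and a brief addition on analysis and follow-up. It needs no extra patients or procedures. It concerns study participation and analysis only, and leaves the care pathway in Section 11 as it stands.
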